163 We hypothesize that, as compared to the actual standard of care transition strategy (1:1 dose
164 conversion at the day of CSII to MDI transition), an alternative transition strategy will result in
165 lower time spent in hyperglycemia without increasing the risk for hypoglycemia. The alternative
166 strategy being (overlap transition strategy):

- 167 • Administration of insulin degludec at a 1:1 basal dose conversion dosage at day 0, with the
168 concomitant use of the insulin pump for 48 hours from transition, where CSII basal rate

169 will be reduced by 50% during the first 24 hours from transition and by 75% during 24 to
170 48 hours from transition. CSII will be disconnected after 48 hours from transition.

171 **3.2. Endpoints:**

172 Primary and secondary endpoints will be analyzed from 1-week of blinded CGM use during
173 randomization phase.

174 Primary endpoint:

175 1. Time spent in CGM glucose levels >180mg/dl

176 Secondary endpoints:

177 1. Time spent in CGM-measured “time-in-range”(glucose levels ≥ 70 mg /dl and ≤ 180 mg/dl)

178 2. Time spent in CGM-measured hypoglycemia < 70 mg/dl

179 3. Frequency of severe hypoglycemia as defined by the ADA (severe cognitive impairment
180 requiring external assistance for recovery) and severe hyperglycemia (BG \geq 250 needing
181 hospitalization)

182 4. Number of boluses (correction boluses) between groups during first 72 hours of
183 randomization

[figure not shown]
184 5. Patient-Reported Outcomes (PRO) using validated questionnaires; insulin delivery
185 satisfaction survey (IDSS) and Work Productivity and Activity Impairment Questionnaire:
186 Specific Health Problem V2.0 (WPAI: SHP) [18,19]

187 **3.3. Study design:**

188 • This is a 3-week, randomized control, open label, single center clinical trial with two study
189 arms comparing the efficacy and safety of the ‘standard of care transition’ and an ‘overlap
190 transition’ strategy

- 191 • The study consists of a screening phase, one week of run-in phase (blinded CGM
- 192 monitoring), one week of the experimental protocol following randomization phase and
- 193 one week of follow-up phase.
- 194 • Overall, the study will last 3 weeks that includes four clinical trial phases (**Figure 1**):
- 195 ○ Screening phase (Week 0): After informed consent, inclusion and exclusion, blinded CGM
- 196 will be inserted.
- 197 ○ Run-in phase (Week 0 to end of week 1): Subjects will wear blinded CGM and continue to
- 198 use CSII.

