- 199 ○ Randomization phase (Week 1 to week 2): Subjects will be randomly allocated to one of
- 200 two transition protocols (1:1 randomization).
- 201 ○ Follow-up phase (Week 2 to week 3): Subjects will return to their preclinical trial CSII
- 202 regimen.

203 **Figure 1:** Study Design
 204

205 **3.4. Rationale for study design**

206 The rationale behind the overlap protocol strategy is linked to insulin degludec pharmacokinetic
207 and pharmacodynamics. Indeed, insulin degludec steady state concentration reaches 60% and 85%
208 respectively at day 1 and 2, and 100% steady state is reached on day 3 from the first day of insulin
209 degludec injection [12-13].

210 Therefore, 50% and 75% dose reduction proposed in the overlap transition strategy of the first 2
211 days will cover for the slow rise of insulin degludec concentration the first 2 days, and the 100%
212 insulin pump discontinuation on day 3 will correspond to the time needed for insulin degludec to
213 reach the steady state. This would reduce time spent in hyperglycemia post-CSII discontinuation.

214 Rationale for blinded CGM: Since the primary outcome is time spent in hyperglycemia (CGM
215 glucose >180 mg/dl), it is necessary to have CGM during randomized phase. Real-time CGM
216 would interfere with the primary and secondary outcomes as patients will have ability to see CGM
217 glucose trend and adjust insulin accordingly. Therefore, blinded CGM would be appropriate for
218 this research protocol. In addition, the time in range (and percentage of hypoglycemia) also
219 depends on person' ability to manage diabetes and therefore, baseline CGM will provide the data
220 about time-in-range and time spent in hyper-and hypo-glycemia. The information from blinded
221 CGM during run-in-phase will be useful for analysis of primary and secondary outcomes that will
222 be adjusted for baseline CGM glucose metrics. Blood glucose fluctuations are greatest during the
223 first week of insulin pump to MDI transition and therefore, 1 week CGM period is enough for
224 comparison of primary and secondary outcomes between the groups.

225 **4. CLINICAL RESEARCH SITES**

226 The study will be conducted at a single site, Barbara Davis Center for Diabetes.

227

228 **5. STUDY POPULATION:**

229 We plan to enroll 34 participants with the expectation that 30 will be randomized and complete the
230 study.

231 **5.1. Inclusion criteria**

232

233 1) Age ≥ 18 years and ≤ 65 years

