- 400 and will start insulin degludec injection (1:1 dose conversion) once a day in the
- 401 morning.

402 ○ Group 2 (overlap transition): Subjects will receive insulin degludec in full dose (1:1
 403 dose conversion) at randomization, and CSII basal rate will be reduced by 50%
 404 during the first 24 hours of the transition and by 75% during 24 to 48 hours of the
 405 transition. CSII will be discontinued on day 3 of the transition.

406 The insulin degludec initiation and CSII basal reduction over 72 hours has been summarized in
 407 Table 2;

408 **Table 2:** CSII changes and MDI initiation by randomization groups
 409

Randomization	Treatment Change	V2 (Day 7±1)	P1 (V2+24 hours)	P2 (P1+24 hours)
Group 1(n=15) Standard of care	CSII	Discontinuation		
	Insulin degludec	Once a day in the morning (1:1 dose conversion)		
	Insulin aspart	Based on carbohydrate ratio and correction factor		
Group 2(n= 15) Overlap transition	CSII	50% basal rate reduction	75% basal rate reduction	Discontinuation
	Insulin degludec	Once a day in the morning (1:1 dose conversion)		
	Insulin aspart	No insulin aspart injections as patients will be using boluses through insulin pump	No insulin aspart injections as patients will be using boluses through insulin pump	Insulin aspart injections based on carbohydrate ratio and correction factor

410

411 ○ Insulin degludec dose conversion guidance:

412 • On the day of randomization, CSII will be downloaded and information on average basal
 413 insulin for the last 3 days, carbohydrate ratio and correction factor will be recorded.

414 • The average basal insulin for last 3 days will be used to calculate insulin degludec U-100
 415 starting dose. For example; average basal insulin during last 3 days of CSII is 20 units/day,
 416 the insulin degludec U-100 starting dose will be 20 units/day. The dose will be rounded up or
 417 down as needed. E.g. if patient’s total daily dose is 32.4 units, it will be rounded to 32 units

418 per day. All subjects will be instructed to use insulin degludec once a day in morning only.
419 The first dose of insulin degludec will be given in the clinics at Visit 2.

- 420 • The dose of insulin aspart will be based on patient’s own carbohydrate ratio and correction
421 factor. Carbohydrate ratio is defined as the number of carbohydrates covered by each unit of
422 rapid acting insulin. Correction factor (aka insulin sensitivity factor) is defined as how much

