- 457 ■ Subjects will be transitioned back to their preclinical trial insulin pump regimen. The same
- 458 basal and bolus settings will be used as of preclinical trial insulin pump settings. However,
- 459 there may be changes made to basal and bolus insulin doses depending on blood glucose
- 460 control during the study period at the discretion of investigators. To reduce the risk of

461 hypoglycemia, subjects will be advised to set a 50% temporary basal insulin rate for 24 hrs
462 following insulin degludec transition.

463 **6.6. Phone call 3, week 3, day 21±1: follow-up phone call and end of the study**

464 ▪ The intention of phone call 3 is to make sure that subjects are not experiencing major
465 hypoglycemia or hyperglycemia events. The study coordinator will make a phone call to
466 assist subjects if they require insulin dose adjustments. AE/ SAE will be recorded, if any,
467 during third week of clinical trial. However, they would not be a part of statistical analysis.

468

469

470

471

472

473

474

475

476

477

478

479

480

481

482

483 **6.7. Table 4: study visit outline**

Period	Screening and Run-In-Phase	Randomization			End of treatment	Follow-up
		V1	V2	P1		
Visits	V1	V2	P1	P2	V3	P3
Day/time from last visit	0	7	V2 + 24hrs	P1 +24hrs	14	21
Time window		±1 day	±6hrs	±6 hrs	±1 day	±1 day
Subject related info/assessment						
Informed consent	X					
Inclusion/exclusion criteria	X					
Screen fail/withdrawal criteria	X	X				
Demography and medical history	X					
Diabetes history	X					
GOLD questionnaire	X					
IDSS, and WPAI questionnaire	X	X			X	
Concomitant illnesses	X					
Review of current medications	X					
Vital signs	X					
BMI	X					
Physical examination	X					
Report AE/SAE	X	X	X	X	X	X
Trial material/steps						
Dispensation of study drugs	X	X				
SMBG and DSM education	X					
Glucose and insulin diary		X	X	X		
Blinded CGM insertion/training	X	X				
Blinded CGM removal/download		X			X	
SMBG profile	X	X				
MDI initiation and training		X				
Randomization		X				
Transition back to CSII					X	
Compliance check		X				
Blood Draw						
POC A1c, urine pregnancy test*	X				X	
CMP (blood sampling)	X					

484 V1, V2, V3 stand respectively for visit 1, 2 3; P1, P2, P3 stand respectively for phone call 1, 2, 3
485 SMBG; self-monitoring of blood glucose, BMI; body mass index, DSM; diabetes self-
486 management education, POC; point-of-care.
487 *pregnancy test only for women in reproductive age.

488
489

490

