491 **6.8. Assessments for Safety:**

492 The following safety assessments will be performed;

- 493 ▪ Time spent in CGM measured hypoglycemia (< 70 mg/dl) and time spent in hyperglycemia
- 494 (≥250 mg/dl)
- 495 ▪ AE/SAE
- 496 ▪ Documented hypoglycemic episodes
- 497 ▪ Height, weight, vitals and physical examination
- 498 ▪ Baseline laboratory assessment
- 499 ▪ Hypoglycemia unawareness assessment (using GOLD questionnaire)
- 500 ▪ Pregnancy test at screening

501 **6.9. Assessments for Efficacy:**

502 The assessment for efficacy is time spent in CGM glucose time-in-range (min/ 24 hours, 70-180
503 mg/dl) during the 7 days of randomization period.

504 **7. EVALUABILITY OF SUBJECTS:**

505 The data for a subject with minimum of 5 out of 7 days of blinded CGM prior to randomization
506 and 5 out of 7 days of blinded CGM after randomization will be evaluable and included for the
507 analysis of primary and secondary objectives.

508 **8. STATISTICAL CONSIDERATIONS:**

509 **8.1. Sample size calculation**

510 In a study by Garg and colleagues, the subjects with T1D on MDI and blinded CGM for first 4
511 weeks of the study spent average of 8.8 hours/day (~528 min/ 24 hours) in CGM defined glucose
512 above 180 mg/dl [21]. Similarly, in the recently published DIAMOND study, subjects on MDI
513 using CGM experienced average of 601 minutes (~10 hours/ day, IQR; 467-793 min) per 24 hours

514 of time spent in hyperglycemia [22]. We assume that subjects in standard of care group would
515 have more hyperglycemia than subjects in overlap transition group. Therefore, the expected CGM
516 hyperglycemia is ~ 650 minutes/24 hours in standard of care and ~ 500 minutes/24 hours in
517 overlap transition group with the differences in CGM glucose by 150 minutes/day between the
518 groups.

519 This study is powered based on the primary endpoint, which is time spent in CGM-measured
520 glucose levels >180mg/dl (hyperglycemia). We have based the sample size on minimal relevant
521 differences between the two treatment groups, using a Type I error rate of 5% and a Type II error
522 rate of 20%. We hypothesize that the primary endpoint, time in minutes spent with glucose levels
523 >180 mg/dl, will be higher in the standard treatment group than in the experimental group (overlap
524 transition group), but we will use a two-sided test to assess differences in hyperglycemia by
525 treatment group. We hypothesize a standard deviation (SD) for time spent in hyperglycemia of

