552 univariate differences between the standard care group and the experimental group for each of the
553 outcomes. Secondary endpoints include time in range (70-180 mg/dl), time spent hypoglycemic
554 (<70 mg/dl), frequency of severe hypoglycemia, number of correction boluses, and patient
555 reported outcomes as defined on the page 7 of the protocol. Secondary endpoints will be
556 examined using student's t-test to compare these outcomes univariately between the standard care
557 and experimental groups. In a sensitivity analysis, CGM metrics will be evaluated in the first 72
558 hours vs entire 1 week as we expect that differences in hyperglycemia and time-in-range will be
559 more pronounced between the two groups in the first 72 hours. For both primary and secondary
560 endpoints, linear regression analysis will be used to examine outcomes by treatment group while
561 adjusting for potential residual confounders, such as age and sex, which may not be fully
562 addressed by randomization. All testing will be two-sided. The analysis will be conducted as an
563 intention-to-treat analysis.

564 **9. DATA HANDLING AND RECORD KEEPING:**

- 565 ▪ All data generated during the study will be retained by the investigator. Safety events will
566 be reported to Colorado Multiple Institutional Review Board (COMIRB) in a timely
567 manner as described under "Adverse Events".
- 568 ▪ Data management is the responsibility of the investigator. All paper and electronic data
569 will be saved in a de-identifiable manner. The data will be stored on BDC computers
570 which are secured by the University of Colorado servers. The data will be accessible only

571 by the study team and if transfer of data needed, appropriate measures, including
572 encryption of data files will be used to ensure security and subject confidentiality.

- 573 ■ The records will be stored securely and kept for minimum of 10 years per the Standards
574 Operating Procedures (SOP) of the University of Colorado [23].
575 [[http://www.ucdenver.edu/research/Research%20Administration%20Documents/COMIRB
-Policy-and-Procedures-Document.pdf](http://www.ucdenver.edu/research/Research%20Administration%20Documents/COMIRB
576 -Policy-and-Procedures-Document.pdf)]

577 **10. ETHICS:**

- 578 ■ The trial will be conducted in compliance with this protocol, ICH GCP, the University of
579 Colorado COMIRB research policy and in accordance with the Declaration of Helsinki
580 [23-25].

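### No use is specified for the baseline IDSS and WPAI scores, which may cost precision in the patient-reported comparison at 15 per arm

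*Combined protocol and SAP*

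**What the plan says.** Secondary endpoint 5 in Section 3.2 is given as "Patient-Reported Outcomes (PRO) using validated questionnaires; insulin delivery" satisfaction (IDSS) and work and activity impairment (WPAI). It defines no score, no visit, and no choice between a Visit 3 value and a change from baseline.

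The Table 4 row "IDSS, and WPAI questionnaire" is marked at V1 (screening), V2 (the randomization visit) and V3 (end of treatment). Section 6.3 describes Visit 2 but does not mention the questionnaires, so their order relative to randomization within that visit is not stated.

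Section 8.2 compares all secondary endpoints by a Student "t-test to compare these outcomes univariately between the standard care" and experimental groups. It then adds a regression for both primary and secondary endpoints, "adjusting for potential residual confounders, such as age and sex, which may not be fully" dealt with by randomization. Section 3.4 separately says that primary and secondary outcomes will "be adjusted for baseline CGM glucose metrics".

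**The concern.** The protocol accepts the principle of baseline adjustment. Section 3.4 justifies the run-in CGM week by noting that glucose outcomes depend on the individual, and commits to adjusting for it. For the patient-reported outcomes the matching baseline is scheduled twice, yet no section says which visit is the baseline or what is done with it. A CGM metric is not the baseline of a satisfaction or work-impairment score, and neither is age or sex.

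Precision is at stake. Section 8.1 puts the detectable effect at 1.06 SD for all endpoints, which is a large difference. Randomization is unstratified with 15 per arm, so some chance imbalance in starting scores is to be expected. There is also a question of pre-specification. In an open-label trial, leaving V1, V2, a change score or no baseline all open until the data are in hand is avoidable analytic freedom.

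**Working it through.** **Inputs from the documents.** 15 completers per arm, 1:1 allocation, two-sided testing, "using a Type I error rate of 5% and a Type II error" rate of 20% (Sections 3.3, 8.1 and 8.2).

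**Step 1: reproduce the plan's figure.** For a two-sample t-test with n per arm, the noncentrality is d·√(n/2) on 2n − 2 = 28 degrees of freedom. Solving for d:
- 80% power: d = 1.0598. Times an SD of 140, 160 or 180 min, this is 148.4, 169.6 or 190.8 min.
- 90% power: d = 1.2264, or 171.7, 196.2 or 220.8 min.

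These match Section 8.1 (1.06 and 1.23). They are figures for an unadjusted t-test, and no number in the plan is disputed.

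**Step 2: add one baseline covariate.** Let r be the within-arm correlation between baseline and V3 score. The residual variance is multiplied by (1 − r²) and the degrees of freedom fall to 27. With 27 degrees of freedom and r = 0, the detectable effect at 80% power is 1.0612. In general it is 1.0612 × √(1 − r²). Chance baseline imbalance multiplies the variance by a further 1 + 1/(30 − 4) = 1 + 1/26, so the effect is multiplied by √1.0385 = 1.019.

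The documents give neither r nor an SD for either questionnaire, so r is shown over a range and effects are in SD units of the V3 score.

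| Assumed r | Detectable effect, 80% power | With imbalance factor | Power at 1.06 SD (with imbalance factor) |
|---|---|---|---|
| 0 | 1.061 | 1.081 | 0.799 (0.784) |
| 0.3 | 1.012 | 1.032 | 0.835 (0.821) |
| 0.5 | 0.919 | 0.937 | 0.898 (0.887) |
| 0.6 | 0.849 | 0.865 | 0.938 (0.929) |
| 0.7 | 0.758 | 0.772 | 0.975 (0.970) |
| 0.8 | 0.637 | 0.649 | 0.997 (0.996) |

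**Step 3: break-even.** Adjustment pays once 1.0814 × √(1 − r²) falls below 1.0598. That requires r² above 1 − (1.0598/1.0814)² = 0.040, so r above about 0.2. Below that, the loss is at most 1.08 against 1.06.

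**Step 4: the change score.** The documents do not exclude a t-test on change from baseline. With equal SDs at both visits its detectable effect is 1.0598 × √(2(1 − r)): 1.499 at r = 0, 1.254 at 0.3, 1.060 at 0.5 and 0.821 at 0.7. A change score is therefore worse than the V3 score alone when r is below 0.5, and worse than regression on baseline at each of these values.

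**The case against.** Several points against the concern are sound.

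- **A reader might infer that the baseline scores are never used, or that the t-test is the only comparison.** The documents do not support this. The Section 8.2 regression covers secondary endpoints, its covariate list gives examples only, and the form of the endpoint is undefined. A change score or a baseline covariate is not ruled out. What stands is that neither is specified.
- **A reader might infer bias.** The unadjusted test is valid under randomization, and its standard error already reflects differences between people and chance imbalance. Giving up real-time CGM or automated mode applies to both arms.
- **A reader might take V2 as a pre-randomization measurement.** Only V1 is clearly so.
- **The gain may be small.** By V3 both arms are on injections, whereas the earlier IDSS rates the pump. The two scores describe different delivery methods, so r could be low. At r = 0.3 the gain is slight, and near zero there is none.
- **A reader might extend the argument to the correction-bolus count (endpoint 4)**, because "On the day of randomization, CSII will be downloaded and information on average basal" insulin over three days is recorded. That does not hold. The recorded items are basal insulin, carbohydrate ratio and correction factor, with no bolus count. Pumps are the participants' own, of any make, and the outcome comes from a paper diary. Such a covariate would be partly missing and measured differently from the outcome.

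It is also fair that the trial is powered on time above 180 mg/dl, and that this is the last-listed secondary endpoint.

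**Conclusion.** The point holds as a gap in specification with a possible cost in precision. Baseline questionnaire scores are scheduled, and the plan assigns them no role and names no baseline visit. If r lies between 0.5 and 0.7, using the baseline score would lower the detectable effect from 1.06 SD to about 0.92 to 0.76 SD (0.94 to 0.77 with the imbalance factor). At r = 0.3 it would be about 1.01 (1.03). At r = 0 it would be 1.06 (1.08), so little is lost if the baseline proves uninformative. These figures assume 15 analysed per arm, a linear relation and equal variances; r is assumed throughout. The primary endpoint and the stated sample size are unaffected. The change is worth making because the data are already scheduled and the cost is close to nil, not because the planned test is invalid.

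**What to change.** In Section 8.2, make the patient-reported analysis a linear regression of the V3 IDSS score, and of each V3 WPAI score, on treatment plus the baseline score of the same questionnaire. State in Section 3.2 that the endpoint is the V3 score.

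Name one baseline visit for everyone before the data are examined: V2 if the questionnaires are completed before the allocation is revealed, otherwise V1 for all participants. Do not mix visits between participants. Add to Section 6.3 that the questionnaires are completed before allocation is disclosed. The summary of protocol changes shows that enrolment had already begun, so if the order at V2 cannot be established for those already randomized, V1 is the safe choice for all.

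The unadjusted t-test can stay as a supporting result. The cost is one degree of freedom per model, one ordering instruction at V2 and a few lines of text, with no new data collection. No bolus-count covariate should be added for endpoint 4.

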Appendix 1: Glucose and Insulin Dose Diary

Glucose and Insulin dose Logbook

Study protocol no-
Study personnel name and contact-
 Phone- email

Subject ID: _____ Date: _____ Day: _____

Time	12am	1	2	3	4	5	6	7	8	9	10	11	12p	1	2	3	4	5	6	7	8	9	10	11	
BG Readings																									
Carbs (Grams)																									
Carb boluses																									
Correction bolus																									
Total Insulin Aspart dose																									

Additional Details:

Breakfast				Lunch				Dinner			
Time	Food Description	amount	Carb gms	Time	Food Description	amount	Carb gms	Time	Food Description	amount	Carb gms
Morning Snacks			Afternoon Snacks			Evening Snacks					

944
 945
 946
 947
 948
 949
 950
 951

952 **Table: Summary of protocol changes and rationale.**

Revisions	Rationale
Email address change (page 1)	Due to domain change at CU Anschutz, email address of the protocol PI was changed
Exclusion criteria 4. (page 10)	Tandem Control IQ is a HCL system that is approved by the US FDA for T1D in December 2019. Therefore, it is added in the exclusion criteria.
Section 5.5 (page 12). Total number of patients required for screening are increased from 34 to 40.	Due to covid related institutional closure and restrictions, we lost data for 1 patient, 1 patient withdrew from study and 4 screen failed, we increased screening sample size to have 30 patients complete the entire study to have adequate power.
Insulin degludec dose conversion guidance (page 18).	A line is added to have clarification that if total insulin dose in last 3 day is rounded for calculation of insulin degludec. E.g. is patient's total daily dose is 32.4, it is rounded to 32.0 and if 32.7, it is rounded to 33.0 units per day.
Sample size calculation (Page 24 and 25)	Typographical errors were corrected on page 24 and 25.
Statistical Methods (Page 26)	Sensitivity analysis of CGM metrics in the first 72 hours vs entire 1 week is added. This is because we expect the differences in hyperglycemia to be more pronounced in the first 72 hours.
Secondary endpoint 4: there was a typographic mistake (page 7)	As stated on page 19, we intended to collect correction boluses information during first 72 hours only.

953
